Each study participant will be contacted by phone 24-72 hours after they were injected with the investigational agent to confirm their well-being and query them about any new adverse events that may have occurred within 24 hours post-injection.

Repeat imaging:

Longitudinal imaging studies may be conducted under protocol ¹⁸F-AV-45-A14, with prior sponsor approval and at the discretion of the investigator. In these studies subjects may have up to two imaging sessions within a 12 month timeframe. Procedures for each day will be identical to those described above.

Evaluation of Imaging:

Images will be evaluated qualitatively and/or quantitatively:

- Images will be visually examined by a trained radiologist or nuclear medicine physician
 who is blinded to the subject diagnosis and will be reported as either Aβ positive or Aβ
 negative.
- SUV for target areas such as frontal cortex, temporal cortex, parietal cortex, posterior cingulate cortex, anterior cingulate and precuneus, and reference regions including cerebellum will be calculated. SUVR for cortical target areas relative to cerebellum will also be calculated.

Statistical Methods:

General Statistical Considerations

All values will be summarized by diagnostic groups. Generally, patients should be classified as Alzheimer's disease (AD), mild cognitive impairment (MCI) or cognitively healthy volunteers in accordance with the classification guidelines in Appendix 11.3. However, alternative criteria may be used if specified in the companion protocol. Frequency distributions including counts and percents will be included for all categorical outcomes. Summary statistics including mean, standard deviation, median, minimum and maximum values will be presented for all continuous outcomes.

Populations for Analysis

IND Sponsor:	Name of Compound:	
Avid Radiopharmaceuticals, Inc.	Injection	(E)-4-(2-(6-(2-(2-(2-[¹⁸ F]fluoroethoxy)ethox y)ethoxy)pyridin-3-yl)vinyl)-N- methylbenzenamine

The efficacy population will include all patients for whom image data are available. All analyses involving amyloid imaging outcomes will be based on the efficacy population. All subjects who receive florbetapir will be included in the safety population.

Efficacy (Imaging Results)

- Qualitative assessment of image (A β + or A β -)
- Quantitative assessment (SUVR) associated with the following brain regions:

Frontal cortex

Temporal cortex

Parietal cortex

Posterior cingular cortex

Anterior cingulate

Precuneus

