Global average of all of the above

Summary statistics will be provided as indicated above.

Demographic, Baseline Characteristics and Cognitive Scales

Frequency distributions and summary statistics for demographic and baseline variables will be presented by diagnostic group and for all subjects combined. Key demographic and baseline characteristics to be summarized include, but are not limited to: age, gender, education, race, and disease history.

Summary statistics for MMSE will be presented by diagnostic group and overall.

Safety Analysis

The number and percentage of subjects who experience adverse events and serious adverse events will be summarized by diagnostic group and total population.

TAE	BLE OF CONTENTS	Page
1.	INTRODUCTION	10
2.	TRIAL OBJECTIVES	12
3.	SPONSOR, INVESTIGATOR(s) AND OTHER PARTICIPANTS	13
4.	TEST DRUG AND CONTROL AGENTS	14
	4.1 Descriptive Name	14
	4.2 Radioactive Labeling	14
	4.3 Decay Characteristics	14
5.	INVESTIGATIONAL PLAN	15
	5.1 Overall Design and Plan of Trial	15
	5.2 Planned Dosage and Duration of Treatment	16
	5.2.1 Dosage and Administration	16
	5.2.2 Rationale for Dosage	16
•	5.3 Selection of Subjects	16
	5.3.1 Inclusion Criteria	16
	5.3.2 Exclusion Criteria	17
	5.4 Prior and Concomitant Therapy	18
	5.5 Removal of Subjects from Trial	19
	5.6 Premature Termination of Trial/Closure of Center	19
6.	WARNINGS/PRECAUTIONS	20
7.	PROCEDURES AND METHODS	20
	7.1 Assessment Periods	20
	7.2 Observations and Measurements	22
	7.3 Protocol for Image Collection & Analysis	23
	7.4 Good Clinical Practice and Monitoring	23
	7.5 Informed Consent and Subject Information	24
	7.6 Documentation	24
	7.7 Adverse Events	25
	7.7.1 Adverse Event Monitoring	25
	7.7.2 Adverse Event Definitions	25
	7.7.3 Adverse Event Documentation	28
	7.7.4 Reporting of Serious Adverse Events	28

Florb	etapir F 1	3: Clinical Protocol: ¹⁸ F-AV-45-A14	Confidentia
8.	STA	TISTICAL ANALYSIS	29
	8.1	General Statistical Considerations	29
	8.2	Populations for Analysis	29
	8.3	Endpoint Definitions	29
	8.4	Analyses	29
		8.4.1 Demographic, Baseline Characteristic	cs
		and Cognitive Scales	29
		8.4.2 Safety Analyses	30
		8.4.3 Qualitative assessment of images	30
		8.4.4 Quantitative assessment of images	30
9.	USE	OF DATA AND PUBLICATION	30
10.	INVE	STIGATOR'S REGULATORY OBLIGATION	NS 31
	10.1	Institutional Review Board (IRB)	31
	10.2	Informed Consent	31
	10.3	Protocol Adherence	31
	10.4	Documents Necessary for Initiation of the Tri	al 32

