2. TRIAL OBJECTIVES

This protocol is designed to standardize imaging studies using florbetapir F 18 PET to provide information on amyloid burden in subjects participating in other studies (companion protocol) such as longitudinal studies of aging and studies of biomarkers for neurodegenerative diseases.

The primary objectives of this protocol are to:

 expand the database of florbetapir F 18 safety, amyloid binding as measured by PET imaging, and long-term outcome in cognitively normal volunteers, patients with AD, patients with MCI, and patients with other neurodegenerative diseases; and provide standardized conditions for florbetapir F 18 use, data collection and analysis to facilitate evaluation of subject's amyloid burden in companion studies including but not limited to longitudinal studies of aging, studies of progressive cognitive impairment and studies of imaging and blood/CSF biomarkers of neurodegenerative disease.

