8. STATISTICAL ANALYSIS

8.1. General Statistical Considerations

All values will be summarized by diagnostic group: cognitively normal volunteers, patients with AD, patients with MCI and where relevant, other disorders as determined by the companion protocol. Guidelines for diagnostic classification of cognitively normal volunteers, subjects with MCI and subjects with AD can be found in Appendix 11.3.

Frequency distributions including counts and percents will be included for all categorical outcomes. Summary statistics including mean, standard deviation, median, minimum and maximum values will be presented for all continuous outcomes.

Additional details concerning statistical analyses will be included in the Statistical Analysis Plan (SAP) to be completed prior to the end of enrollment into the study.

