8.4. Analyses

8.4.1 Demographic, Baseline Characteristics and Cognitive Scales

Frequency distributions and summary statistics for demographic and baseline variables will be presented by diagnostic group and for all subjects combined. Key demographic and baseline characteristics to be summarized include, but are not limited to: age, gender, education, race, and disease history.

Summary statistics for MMSE will be presented by diagnostic group and overall.

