5. CLINICAL ASSESSMENTS

5.1. Screening and Baseline Assessments

There are many clinical assessments data collected in companion protocols. For the safety evaluation purpose of this protocol, the following screening and baseline assessments will be included:

- 1). Subjects' birth year, sex, race, ethnicity, and education;

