8. BASELINE PATIENT DATA

8.1. Baseline Demographic and Physical Characteristics

Frequency distributions and summary statistics for demographic and baseline characteristics will be presented all subjects in the Safety population.

Demographics and baseline characteristics will be also presented in listings.

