10.1. Adverse Event Preferred Term and Body/Organ System Summary Tables

In this study, an Adverse Event (AE) is defined as any undesirable experience occurring to a subject after an injection of florbetapir F 18, whether or not it is considered as related to the investigational product. Laboratory test abnormalities considered by the Investigator to be clinically relevant should be reported as AEs. For this protocol, treatment-emergent AEs (TEAE) are considered as any undesirable experiences, signs, or symptoms that begin or worsen in intensity or frequency at the time of or after the administration of study drug, and within 48 hours since study drug injection. These will be recorded on the AE pages.

The incidence of AEs will be presented overall by system organ class (SOC) and by preferred term. Incidence of AEs by severity and relationship to study medication will also be presented. Adverse events resulting in discontinuation from the study and the incidence of serious adverse events (SAE) will be summarized.

Pre-existing conditions (i.e., undesirable experiences, signs, or symptoms that begin prior to the Screening Visit) will be recorded on the medical history and/or physical exam pages and will not be summarized in this study.

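### The SAP pools its AE, SAE and baseline tables where the protocol specifies them by diagnostic group, and gives no reason for the change

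*SAP*

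**What the plan says.** **Protocol.** The Safety Analysis paragraph of the synopsis states that adverse events and "serious adverse events will be summarized by diagnostic group and total population". Protocol 8.1 sets the general rule: "All values will be summarized by diagnostic group". It names cognitively normal, AD and MCI subjects and, where relevant, other disorders. Protocol 8.4.1 asks for demographic and baseline variables by group and combined, and adds that "Summary statistics for MMSE will be presented by diagnostic group and overall". The first primary objective (Protocol 2) is to enlarge the database on safety, amyloid binding and "long-term outcome in cognitively normal volunteers, patients with AD, patients with MCI, and patients with other neurodegenerative diseases". Protocol 8.4.2, the section on safety analyses, does not itself mention grouping.

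**SAP.** Section 10.1 says: "The incidence of AEs will be presented overall by system organ class (SOC) and by preferred term". Section 10.1.1 describes one TEAE table by SOC and preferred term, a second by preferred term only, and summaries by relationship and severity. Section 10.1.3 plans an SAE table by SOC and preferred term. Under section 8.1, demographic and baseline summaries "will be presented all subjects in the Safety population". The only baseline items listed in section 5.1 are "birth year, sex, race, ethnicity, and education"; diagnosis and MMSE are not among them. No section of the SAP defines or uses a diagnostic group.

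**The concern.** The SAP narrows the report to safety, and grouping by diagnosis is part of the protocol's plan for safety. Dropping the imaging analyses therefore does not account for dropping the groups.

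The study enrolls through companion protocols and sets no target split by diagnosis. A single pooled AE rate is an average whose weights are whatever case mix those studies supplied. A reader of the planned tables could not tell whether events cluster in one of the populations named in the objective, or how many subjects of each kind were exposed. There is no control arm, so a difference between groups could not by itself be attributed to the tracer, but it should be visible.

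**Working it through.** The documents contain no sample-size or error-rate calculation on this point, so there is no figure to reproduce. The check is a comparison of texts, followed by an illustration of what pooling hides.

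**1. The two documents side by side**

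| Output | Protocol | SAP |
|---|---|---|
| Subjects with any AE or SAE | By diagnostic group and total (synopsis); general rule in 8.1 | Overall (10.1); no group columns (10.1.1, 10.1.3) |
| AEs by SOC and preferred term | 8.4.2 is silent on grouping; general rule in 8.1 applies | Overall (10.1, 10.1.1) |
| Demographics and baseline | By group and combined (8.4.1) | All safety subjects (8.1) |
| MMSE | By group and overall (8.4.1) | Not listed (5.1) |

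**2. Whether the SAP explains the change.** It gives reasons for omitting imaging (3 and 9), the enrolled population (6.1.1), concomitant medications (8.2) and vital signs (10.4). Section 5.1 ties its short variable list to the safety purpose, which is a reason of sorts for leaving out MMSE. None of these is a reason for pooling across diagnoses.

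**3. What a pooled rate hides (illustration).** The total of 1,800 is the protocol's approximate enrollment. All rates and shares are assumed: 3% of subjects with a TEAE outside one group, and a rate r of 6% to 12% in a group making up a share s of 10% to 30%.

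Pooled rate = s × r + (1 − s) × 3%

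| Share s | r = 6% | r = 9% | r = 12% |
|---|---|---|---|
| 10% (180) | 3.3% | 3.6% | 3.9% |
| 20% (360) | 3.6% | 4.2% | 4.8% |
| 30% (540) | 3.9% | 4.8% | 5.7% |

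Two cells give the same answer:

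- 0.30 × 6% + 0.70 × 3% = 1.8% + 2.1% = 3.9%
- 0.10 × 12% + 0.90 × 3% = 1.2% + 2.7% = 3.9%

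A twofold excess in 540 subjects and a fourfold excess in 180 look identical in the pooled table.

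**4. What zero SAEs would exclude (illustration).** With no events in n subjects, the exact two-sided 95% upper bound is 1 − 0.025^(1/n). The group sizes are assumed.

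| n | Upper bound |
|---|---|
| 1,800 (all) | 0.205% |
| 600 | 0.613% |
| 300 | 1.22% |
| 100 | 3.62% |

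The bound for all subjects does not carry over to each population. The planned tables do not give the group denominators needed to work out the others.

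**The case against.** **The SAP may not intend to pool.** In 10.1 the word *overall* precedes a sentence on severity and relationship, so it could mean not split by those factors. Section 6 bases percentages on treatment groups, which implies columns of some kind, and section 2 says the SAP is to be read with the protocol. These readings are possible. However, the study has one agent and no arms, diagnosis is never named, and 8.1 refers plainly to all subjects. Followed as written, the SAP produces no grouped table.

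**The protocol's own basis is uneven.** Section 8.4.2 is silent on grouping, while 8.4.1, 8.4.3 and 8.4.4 state it. The synopsis asks by group only for the number and percentage with AEs and SAEs, so grouping by SOC and preferred term rests on 8.1 alone. That is correct, but nothing in 8.4.2 cancels the rule in 8.1.

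**The illustration proves little.** Any weighted average can arise from different mixtures, and the documents do not suggest that AE rates depend on diagnosis. If the pooled SAE count is zero, every group's count is zero and only the denominators are missing. This stands: the figures show what cannot be read from the tables, not that an excess exists.

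**The groups may be hard to form.** Appendix 11.3 uses CDR and a psychometric battery, which are not in this protocol's screening list or flow chart. It also has no class for a cognitively normal subject with an MMSE of 25 to 28. Companion studies may use other criteria, so groups could be heterogeneous. This stands as a cost and is the reason for an unclassified column.

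**Listings are planned.** AE, SAE, fatal-event and baseline listings are specified, but none is said to carry diagnosis, and a listing does not replace a summary table.

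**Conclusion.** The concern holds. The protocol specifies AE, SAE, baseline and MMSE summaries by diagnostic group. The SAP plans only pooled AE, SAE and baseline tables, omits diagnosis and MMSE, and does not say why the groups were dropped. This rests on the text of the two documents and needs no assumption.

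The consequence is a loss of information about the populations in the primary objective. Its practical size is unknown because the documents give neither AE rates nor group sizes. The total-population rates, which the protocol also asks for, are unaffected, and no test or error rate of the planned safety analysis is involved. The point should be corrected before reporting, but it does not threaten the validity of the data.

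**What to change.** - **Tables.** In SAP 8.1, 10.1.1 and 10.1.3, add columns for cognitively normal, MCI, AD, other or unclassified, and total.
- **Denominator.** In SAP 6, replace the treatment-group wording: each percentage is based on the safety-population subjects in that column.
- **Variables.** Add diagnosis and MMSE to SAP 5.1 and 8.1.
- **Source of diagnosis.** Use the companion protocol's criteria where it specifies them, since the protocol synopsis says that "alternative criteria may be used if specified in the companion protocol". Otherwise use Appendix 11.3. Show subjects who fit no class, or who lack the data, as unclassified.
- **Interpretation.** Present the group columns as descriptive, without causal claims.

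If grouping proves infeasible, the SAP should say so and justify the departure from the protocol. That would be transparent, but it would not recover the information.

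**Cost.** Mostly extra table columns. Diagnosis may have to be drawn from companion-study records, some groups will be small with imprecise rates, and the unclassified column may be sizeable. MMSE is already a screening item, or may be taken from a companion or clinic visit within 30 days.

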10.1.1. Summaries of Adverse Event Incidence Rates for All Patients

All treatment-emergent AEs will be presented in a summary table, by SOC and preferred term. At each level of summarization, a subject will only be counted once per SOC or preferred term. For example, if a subject reports multiple TEAEs with the same SOC, then that SOC will only be incremented by one. As with the SOC, if a subject reports multiple AEs with the same preferred term, then that preferred term will only be incremented by one since subject counts will be presented. AEs will be presented in descending order of frequency. An additional table will present TEAEs in descending frequency by preferred term only. TEAEs will also be summarized by relationship to study drug, and by severity.

All AEs will also be presented in a listing.

10.1.2. Missing and Partial AE Onset Dates

In the event that only a partial end date (month/year) is available, and month/year occurs before that of study drug injection date, the adverse event will be considered as non-treatment-emergent. However, if the onset date is a partial date (month/year) and month/year occurs on or after that of study drug injection date, the following cases will be considered:

- If month/year of the onset date is greater than the month/year of study drug injection date, the adverse event will be considered treatment-emergent;
- If month/year of the onset date is equal to the month/year of study drug injection date, and the end date is present, the end date will be used to determine when the adverse event

resolved. If the end date is on or after study drug injection date, the adverse event will be considered treatment-emergent; otherwise, if the adverse event stopped before study drug injection date, then it will not be treatment-emergent;

- If month/year of the onset date is equal to the month/year of study drug injection date, and the end date is a partial date, the adverse event will be considered treatment-emergent.

10.1.3. Summaries of Adverse Incidence Rates for Serious Adverse Events (SAE), Adverse Event Dropouts, and Death

A serious adverse event (SAE) is an AE that is fatal or life-threatening, or results in hospitalization, prolongation of hospitalization, persistent or significant disability/incapacity, or a congenital anomaly/birth defect. A life-threatening AE is an AE that, in the view of the investigator, places the subject at immediate risk of death from the reaction as it occurred. Important medical events that may not result in death, be life-threatening, or require hospitalization may be considered SAEs when, based upon appropriate medical judgment, they may jeopardize the subject or subject and may require medical or surgical intervention to prevent one of the outcomes listed in this definition.

If there are any SAE, they will be presented by system organ class and preferred term in a table and a listing. All AEs collected with an outcome of “Fatal” will be presented in a listing.

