With prior sponsor approval and at the discretion of the investigator, a subgroup of not more than 5 subjects will be given the option of having a regimen of arterial blood sampling with up to 70 minutes of imaging beginning immediately after florbetapir F 18 administration. See Appendix 11.4 for detailed instructions on arterial blood sampling.

A separate subgroup of subjects, with prior sponsor approval and at the discretion of the investigator may have up to two imaging sessions within a 12 month

timeframe. Adverse events will not be collected during the time between the first follow-up phone call and the second imaging session.

Images will be evaluated qualitatively and/or quantitatively. For qualitative evaluation, images will be visually examined and will be classified as Aß+ (amyloid positive) or Aß- (amyloid negative). For quantitative evaluation, standard uptake values (SUV) will be calculated for cortical target areas (frontal cortex, temporal cortex, parietal cortex, precuneus, anterior and posterior cingulate) and the cerebellum. SUV ratios (SUVR) for cortical target areas relative to the cerebellum will also be calculated and a global mean SUVR will be calculated from the average across all cortical target areas.

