- With prior sponsor approval and at the discretion of the investigator, a subgroup of not more than 5 subjects will be given the option of having a regimen of arterial blood sampling with up to 70 minutes of imaging beginning immediately after florbetapir F 18 administration. See Appendix 11.4 for detailed instructions on arterial blood sampling;
- Subjects will be observed continuously for signs of adverse events or serious adverse events;
- The injection site will be observed for excessive inflammation or damage to the surrounding tissue where the dose was injected; and
- A physician or physician designee will see the patient prior to dosing and prior to discharge.

Follow-Up:

Each study participant will be contacted by phone 24–72 hours after they were injected with the investigational agent to confirm their well-being and query them about any new adverse events that may have occurred within 24 hours post-injection.

Repeat Imaging:

Longitudinal imaging studies may be conducted under protocol ¹⁸F-AV-45-A14, with prior sponsor approval and at the discretion of the investigator. In these studies subjects may have up to two imaging sessions within a 12 month timeframe. Procedures for each day will be identical to those described above.

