7.7.2. Adverse Event Definitions

Adverse Events (AE)

An AE is any undesirable experience occurring to a subject during a clinical trial, whether or not considered related to the investigational product.

For reporting purposes, Avid will distinguish among pre-existing conditions, trial-emergent AEs, and treatment-emergent AEs. The end of study for the purpose of adverse event reporting is defined as 24 hours after administration of florbetapir F 18 injection.

Pre-existing conditions (i.e., undesirable experiences, signs, or symptoms that begin prior to the Screening Visit) will be recorded on the medical history and/or physical exam pages. These conditions will not be entered on the AE pages unless they worsen in intensity or frequency after the Screening Visit and before the Imaging Visit.

Trial-emergent AEs are undesirable experiences, signs or symptoms that begin, or worsen in intensity or frequency, on or after the Screening Visit, and prior to administration of study drug at the imaging visit. These will be recorded on the AE pages.

Treatment-emergent AEs are undesirable experiences, signs, or symptoms that begin or worsen in intensity or frequency at the time of or after the administration of study drug, defined in this protocol as 24 hours after florbetapir F 18 injection. These will be recorded on the AE pages.

Serious Adverse Event (SAE)

An SAE is any AE from this study that results in one of the following outcomes or constitutes one of the following events:

- Death:
- Initial or prolonged inpatient hospitalization (other than that required by protocol; "social hospitalization" or any hospitalization for non-medical reasons does not constitute an SAE);
- A life-threatening experience (that is, immediate risk of dying);
- Persistent or significant disability/incapacity;
- Congenital anomaly/birth defect;
- Occurrence of seizure or seizure-like event:
- Considered significant by the investigator for any other reason.

Important medical events that may not result in death, be life-threatening, or require hospitalization may be considered serious adverse drug events when, based upon appropriate medical judgment, they may jeopardize the patient and may require medical or surgical intervention to prevent one of the outcomes listed in this definition.

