Serious adverse event (SAE) collection begins after the patient has signed informed consent and has received the investigational product. An SAE spontaneously reported to have occurred within 24 hours of florbetapir F 18 administration will be reported, regardless of the investigator's opinion of causation. Thereafter, SAEs are not required to be reported unless the investigator feels the events were related to either investigational product or drug delivery system, or a protocol procedure

Unexpected Adverse Event

An unexpected AE is an AE not previously reported or an AE that occurs with specificity, severity or frequency that is not consistent with the current investigator's brochure.

Relationship to Investigational Product

The assessment of the relationship of an AE to the administration of the study drug (remote, possible, and probable) is a clinical decision based on all available information at the time of the completion of the CRF. The following definitions of the relationship between the study drug and the AE (including SAEs) should be considered:

• Remote (unlikely, doubtful, improbable):
Another cause (concomitant drugs, therapies, complications etc.) is probable.

• Possible:

The time course between the administration of the study medication and the occurrence or worsening of the AE is consistent with a causal relationship but another cause (concomitant drugs, therapies, complications etc.) cannot be ruled out;

or

The time course between the administration of the study medication and the occurrence or worsening of the AE is not consistent with a causal relationship but no alternative cause can be identified.

• Probable:

The time course between the administration of the study medication and the occurrence or worsening of the AE is consistent with a causal relationship and no other cause can be identified (concomitant drugs, therapies, complications etc.).

If the Investigator is unable to assess causality, the AE should be considered "Possible" by definition and not "Remote".

Intensity/Severity of an Adverse Event

In addition to assessing the relationship of the administration of the investigational product to AEs, an assessment is required of the intensity (severity) of the event.

The following classifications should be used:

Mild:

A mild AE is an AE, usually transient in nature and generally not interfering with normal activities.

• Moderate:

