7.7.3. Adverse Event Documentation

All AEs must be fully recorded on the Adverse Event Page of the Case Report Forms. Documentation must be supported by an entry in the subject file. Signs and symptoms of each AE should be described in detail (e.g., start and stop dates, severity, intensity, relationship to investigational product, action taken, and outcome).

Adverse events fulfilling the definition of an SAE should also be recorded on the Serious Adverse Event Reporting Form.

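### The SAP's partial-date rule counts any month-only AE onset in a later month as treatment-emergent, with no upper limit, against its own 48-hour TEAE window

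*SAP*

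**What the plan says.** SAP section 10.1 limits a treatment-emergent adverse event (TEAE) to one that starts or worsens "at the time of or after the administration of study drug, and within 48 hours since study drug injection".

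SAP section 10.1.2 then classifies events with incomplete dates. When the onset is known only to the month and that month is later than the injection month, the first bullet reads: "If month/year of the onset date is greater than the month/year of study drug injection date, the adverse event will be considered treatment-emergent". The two remaining bullets cover an onset in the injection month. With a complete end date, the event is emergent unless it ended before injection. With a partial end date, it is always emergent. Nothing in 10.1.2 refers to the 48 hours.

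The flag drives the main tables of SAP section 10.1.1, by system organ class and preferred term and by preferred term alone. In addition, "TEAEs will also be summarized by relationship to study drug, and by severity".

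The protocol uses a different window. Section 7.7.2 has treatment-emergence "defined in this protocol as 24 hours after florbetapir F 18 injection". Section 7.1 also allows repeat imaging: "In these studies subjects may have up to two imaging sessions within a 12 month timeframe".

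**The concern.** When the day is missing and the month leaves the question open, a rule that errs towards inclusion is ordinary practice. Here the month usually closes the question, and the rule overrides it. The less precise record then gets the opposite class from the precise one. After a single injection on 3 March, an onset of 12 April is not a TEAE, but an onset recorded only as April is.

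The rule also speaks of one injection date, as does the study-day definition in SAP section 6. It does not say which date applies to a subject imaged twice.

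This SAP drops the efficacy analyses, does not summarise vital signs or concomitant medications, and has no laboratory data. Adverse events are the only outcome analysed, so the TEAE flag should follow its own definition. What is at stake is an over-count in the TEAE tables, including those by relationship and severity.

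**Working it through.** This is a check of date logic. The plan gives no figure to reproduce beyond the two windows.

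**Inputs**
- TEAE window: 48 hours (SAP 10.1); 24 hours (Protocol 7.7.2).
- Partial-date rule: onset month later than injection month means emergent, with no limit (SAP 10.1.2).
- Planned enrolment: about 1,800 (Protocol 5.1).
- Number of month-only onsets: not given. Assumed range for misclassified events: 0 to 5.

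**Step 1. When can a later-month onset lie in the window?** Injection date plus 2 days must fall in a later month, so the injection must be on one of the last two days of a month. For 24 hours, it must be on the last day.

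| Window | Dates that can reach the next month | Dates that cannot |
|---|---|---|
| 48 h | 12 × 2 = 24; 24/365 = 6.6% | 341/365 = 93.4% |
| 24 h | 12 × 1 = 12; 12/365 = 3.3% | 353/365 = 96.7% |

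Listing every date of 2013 gives these counts. The leap year 2016 gives the same 24 and 12 dates out of 366. No date reaches a month beyond the next one.

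**Step 2. How much of the next month is reachable?** Even from a month-end injection the 48-hour window touches at most days 1 and 2. That is 2/31 = 6.5% to 2/28 = 7.1% of the month. The rule accepts the whole month and every month after it. An onset in the next month alone can be up to about 62 days after injection.

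**Step 3. The example.** Injection 3 March, so the window closes on 5 March. The earliest possible April onset is 1 April, more than 28 days after injection. No day in April qualifies, yet the rule says emergent.

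**Step 4. The same-month bullets.** The window always overlaps the injection month, so treating unresolved same-month onsets as emergent is consistent with the definition. The gap there is different: neither bullet covers an absent end date.

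**Step 5. Two injections.** Take injections on 3 March and 20 September and a month-only onset of September that ended on 10 September. Measured from the first injection, the first bullet makes it emergent. Measured from the second, the same-month bullet makes it non-emergent. The SAP does not choose.

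**Step 6. Which events can reach the rule?** Protocol 7.7.2 ends AE reporting at 24 hours, and the follow-up call in 7.1 asks only about that period. For subjects imaged twice, section 5.1 adds: "Adverse events will not be collected during the time between the first follow-up phone call and the second imaging session". The main remaining route is a late SAE. After 24 hours, "Thereafter, SAEs are not required to be reported unless the investigator feels the events were related to either investigational product or drug delivery system"; relation to a protocol procedure also qualifies. Section 7.7.3 puts all AEs on the AE page and adds: "Adverse events fulfilling the definition of an SAE should also be recorded on the Serious Adverse Event Reporting Form". A late related SAE without an onset day would then enter the TEAE tables.

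**Step 7. Size.** One event adds at most one subject to a row: 1/1,800 = 0.056 percentage points. Five events: 5/1,800 = 0.28 points.

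**The case against.** The best case against is that the rule rarely does any harm. For routinely collected events, the collection limits mean a later-month onset should arise only from a month-end injection, which is where the rule and the 48-hour window agree. The 93.4% is therefore no measure of effect. The remaining route needs an SAE after 24 hours, judged related, with no onset day, although the protocol asks for start dates and for CRFs to be verified against source. Because section 7.7.2 closes AE reporting at 24 hours, no sentence says outright that such an SAE goes on the AE page. The error can only add events, never hide them. The report is descriptive, with no test or threshold.

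Most of this stands as an argument about size. The number of affected events may well be zero, and the shares of dates must not be read as shares of events. The AE-page step is an inference, but section 7.7.3 supports it, since the SAE form is in addition to the AE page.

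It does not remove the conflict. Conservatism justifies inclusion when timing is unresolved, and a known month outside the window resolves it. The 24- versus 48-hour discrepancy is a separate matter that can also affect fully dated events. It enters here only because the corrected rule needs one limit.

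**Conclusion.** The concern holds. The first bullet of SAP 10.1.2 contradicts the definition in SAP 10.1, and nothing else in the SAP caps it. For a given injection it gives the wrong class to a later-month onset on 341 of 365 injection dates. On the other 24 it is right only if the true onset was in the first day or two of the next month and within 48 hours of injection.

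The numerical effect is probably small: 0 to 0.28 percentage points on the any-TEAE rate, assuming 0 to 5 misclassified events in different subjects and 1,800 subjects in the safety population. The SAE table in SAP 10.1.3 is not restricted to TEAEs and is unaffected, and the AE listing would still show the event. Confidence is high on the inconsistency. The documents do not allow an estimate of how many events it touches.

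**What to change.** Replace the bullets of SAP 10.1.2 with one overlap test:

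- A partial-dated event is treatment-emergent only if its possible onset range overlaps the TEAE window after any florbetapir injection the subject received, and its end date, if known, is not before that injection.
- A later-month onset then counts only when the first day of that month falls in an injection's window, or when a second injection makes the ranges overlap.
- Keep unresolved same-month onsets as emergent, and extend this to events with no end date.
- In the opening sentence, which now deals only with a partial end date, add that a partial onset in a month before injection is non-emergent unless worsening within the window is recorded.
- Reconcile the SAP's 48 hours with the protocol's 24 hours so that the test has one limit.

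The cost is one paragraph in the SAP and a small change to the derivation code. No new data are needed and there is no burden on patients.
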